1.2 STANDARD TREATMENT FOR EARLY STAGE CANCER OF THE ORAL CAVITY

Surgery and radiotherapy are standard treatment modalities for T1/T2 oral cavity cancer (OCC).⁴ Several studies demonstrated that surgery is the preferred treatment for oral squamous cell carcinoma (SCC), yielding superior 5-year survival rates when compared to radiation therapy.^{4,5} Furthermore, the sequelae of radiation therapy such as xerostomia, chronic dental decay and risk of mandibular osteonecrosis remain long after the patient is “cured,” reducing the patients’ quality of life (QoL).⁶

Effective surgical treatment of OCC requires wide local resection of the primary tumor with clear surgical margins. In order to secure tumor free margins the surgical procedures remove additional functional tissue often affecting speech and swallowing. **Following the initial surgery, the risk of local recurrences is as high as 20%.**⁷⁻⁹ Local recurrences are usually treated with further surgery, requiring more mucosal resection. Patients that have been cured with standard therapy also have a significant risk of developing second primary tumors, which has been associated with poor prognosis.¹⁰⁻¹² Treatment of second primaries will increase patient morbidity. Currently, younger patients are being diagnosed with oral cancer, and their QoL is severely affected by standard of care therapies.^{6,13} It is important to provide this patient population with a first line therapy that will not cause irreversible long-term toxicities, and if failed, can be followed with standard surgery to improve the chance of cure.

Photodynamic therapy (PDT) can result in good local control of early stage OCC with minimal loss of tissue volume and excellent long-term healing that is expected to improve QoL.¹⁴⁻¹⁶ Our experience (including our collaborator, [name]) suggest that patients who failed to respond to PDT can be safely salvaged with standard surgery.^{17,18}

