2 RATIONALE

Surgical resection and radiotherapy are front line therapies for T1 and T2 oral cavity cancer. However, these therapies are associated with multiple morbidities and impaired QoL issues such as alteration of speech, dysphagia and xerostomia. PDT, which involves the activation by light of

a tumor-localized photosensitizer, has proven to be an effective local treatment for a range of solid tumors. It has the potential to become an effective first line treatment modality for this disease for the following reasons: it is minimally invasive, has low toxicity, is not associated with any long-term morbidity and is repeatable. Importantly, it allows the physician to reserve conventional, more toxic treatments such as radiotherapy and chemotherapy for later application, if needed.

The purpose of this multicenter study is to test the non-inferiority of PDT with HPPH to standard of care by comparing the rate of tumor response and QoL after PDT to those obtained after surgery in participants with previously untreated T1/T2 N0 SCC of the oral cavity.

Phase I studies have demonstrated that this treatment is safe. These studies also determined the safe drug and light dosages: 4 mg/m² and 100 - 140 J/cm², respectively. Data also suggest that early stage SCC may have excellent response to this therapy (see **Table 1**).

In our recent study with HPPH-PDT, all the patients with T1/T2 who failed to have CR to PDT were successfully salvaged with surgery.¹⁸ Importantly, in patients with invasive disease who achieved only PR, the disease could be downgraded to dysplasia, thus minimizing salvage surgery. While all studies with HPPH-PDT to date have been Phase I studies, the response to PDT is swift and all patients, with few exceptions, have been assessed for response by pathological analysis.

We believe that PDT with HPPH is a viable option to treat patients with T1/T2, because:

- HPPH-PDT is expected to be an organ sparing treatment option, and failures can be salvaged with surgery.
- HPPH, at clinically effective antitumor doses, is associated with significantly reduced cutaneous photosensitivity that rapidly declines over several days.⁴¹
- The CR to HPPH-PDT is expected to be 85%, which would be comparable to cure rates after the initial surgery that is associated with 20% local recurrence.⁷⁻⁹
- Noninvasive optical spectroscopy has potential to serve as a surrogate reporter for tumor response to HPPH-PDT.⁴⁸

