4.1.1 Treatment Procedure

Figure 1. Study Schema

For those participants randomized to HPPH with PDT, a single dose of HPPH at 4 mg/m² will be administered via slow intravenous (IV) infusion over 1 hour. Approximately 24 hours (\pm 4 hours) later, the target tumor will be illuminated with a 665 \pm 3 nm laser (ML7710-665 LASER, Modulight, Inc., Tampere, Finland). A total light dose of 140 J/cm² at a fluence rate of 150 mW/cm² will be delivered with a single quartz fiber optic equipped with a micro lens (Frontal Light Distributor Model FD1, Medlight SA, Switzerland). In areas that preclude direct illumination of the lesion and margins with a microlens fiber, the light will be delivered through a cylindrical diffuser fiber with a diffuser end (Medlight SA, Switzerland) that will be inserted into a 10 mm in diameter flexible applicator (Frieburg Flap, Elekta Inc. Atlanta, GA). The Frieburg Flap is an FDA approved device designed to keep radiation source at constant distance from the treatment surface (see attached letter of approval). Multiple cylindrical fibers (in parallel) can be inserted into the flap to cover an entire tumor and margins in curved surfaces. The light through each cylindrical diffuser will be delivered at a fluence rate of 495 mW/cm (accounting for about 5% loss) to a total light dose of 462 J/cm, which is equivalent to surface illumination of 150 mW/cm² and 140 J/cm². The PDT center at RPCI will provide sections of the Frieburg Flap that will need to be sterilize prior to use, following the manufacturer instructions (see attached). The entire tumor and 5 mm - 10 mm margins will be illuminated. The remainder of the oral cavity will be shielded to avoid illumination of healthy tissue.

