4.3 MANAGEMENT OF THE NECK AND SALVAGE SURGERY

The management of the neck will be according to standard of care, at the discretion of the treating surgeon. If the participant, based on the pathology of the neck dissection or primary oral cancer resection, has perineural invasion, extracapsular spread, or requires additional therapies including radiation or chemotherapy, they will be dropped from the study and replaced with another participant.

Participants will receive standard curative therapy 6 weeks after failing to respond to PDT with HPPH. All the participants who will have disease progression, local recurrence, or partial or no response (PR, NR) following the PDT with HPPH will be considered treatment failures. The determination will be performed during the study visits, and based on clinical exam and pathology, if clinical exam is unclear.

The surgeon will provide a surgical plan for every patient, including those randomized to PDT. If the patient requires salvage surgery post-PDT, the surgeon will compare the salvage surgery specimen diameter to the diameter of the spot size used for PDT. This data will be used to demonstrate whether PDT affects the surgical plan.

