Under the null hypothesis ($\pi_{PDT} = \pi_{SOC} - \Delta = \pi$) is the probability of observing a particular set of results. A non-inferiority margin of 20 percentage points will be utilized and the Farrington-Manning based test will be performed in conjunction with a 0.05 nominal significance level. In the event that the non-inferiority test is statistically significant, a test for superiority will be conducted. The samples sizes of the trial are set at 57 in the standard of care and PDT groups. With the proposed sample sizes, there is approximately 80% power associated with the non-inferiority test when the true tumor response probabilities are equal to 85% in both groups. The calculation was carried forth using SAS PROC POWER.

In the analysis of QoL simple data analyses will initially take place including individual participant-level profile plots and overall mean plots used to examining the mean structure. Formal statistical examination of longitudinal patterns will be done through the use of a mixed model. Restricted maximum likelihood estimation will be utilized in the model fitting procedures as implemented by SAS PROC MIXED (version 9.3). Once the model is fit, specific linear contrasts based on the estimated model parameters will be constructed and used to test hypotheses concerning between time points and between group comparisons. We acknowledge the possibility of informative missingness, that is, the probability of a particular observation being missing may be related to the health of the participant, and therefore analyses will be interpreted with caution. All tests will be two-sided and tested at a 0.05 nominal significance level. Standard diagnostic plots will be used to assess model fit and transformations of variables may be considered in order to meet statistical assumptions.

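### Section 4.3 measures the salvage specimen against the PDT light spot, at best a rough proxy for the participant's own planned resection, so a change of plan cannot be separated from a difference in margins

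*Combined protocol and SAP*

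**What the plan says.** Three consecutive sentences in Section 4.3 set up this item. The first collects the plan: "The surgeon will provide a surgical plan for every patient, including those randomized to PDT". The second gives the comparison to be made at salvage: "the surgeon will compare the salvage surgery specimen diameter to the diameter of the spot size used for PDT". The third gives its purpose: "This data will be used to demonstrate whether PDT affects the surgical plan".

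Section 4.1.1 determines the size of the light field: "The entire tumor and 5 mm - 10 mm margins will be illuminated". Where the lens fiber cannot illuminate the lesion directly, the flap applicator is used, and "Multiple cylindrical fibers (in parallel) can be inserted into the flap to cover an entire tumor and margins in curved surfaces".

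On the extent of surgery, Section 1.2 says only this: "Effective surgical treatment of OCC requires wide local resection of the primary tumor with clear surgical margins". No width in millimeters appears there or elsewhere.

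The comparison is not among the primary, secondary or tertiary objectives (Sections 3.1 to 3.3), and Section 12 contains no analysis of it.

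**The concern.** The purpose sentence asks about a departure from the plan. The plan is collected, yet it is not a term in the one comparison that is written down. The light spot takes its place, and its size follows from the illumination margin, not from what the surgeon meant to remove. A salvage specimen larger or smaller than the spot can reflect a change in surgery, a difference between the light margin and the surgical margin, or both. The written comparison cannot tell these apart.

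What is at stake is modest but real. Section 2 says that earlier patients with only a partial response could have smaller salvage operations, and Section 12.1 relies on effective salvage when discussing safety. This is the only check in the protocol of whether PDT changes the extent of later surgery. Its purpose sentence promises a demonstration, which is more than the comparison can deliver.

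**Working it through.** The plan gives no sample size, effect size or test for this item, so there is no stated figure to reproduce. The check is a short piece of geometry plus a count of expected cases.

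**Inputs**
- Light margin, m_spot: 5 to 10 mm (Section 4.1.1).
- Planned surgical margin, m_plan: not given. Assumed here to lie in the same 5 to 10 mm range.
- Pre-treatment tumor diameter: d. It cancels below.
- PDT arm size: "The samples sizes of the trial are set at 57 in the standard of care and PDT groups" (Section 12.2).
- PDT response: "The CR to HPPH-PDT is expected to be 85" percent (Section 2), so about 15% failures.

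**Geometry**, taking both fields as circles centered on the tumor:
- Spot diameter = d + 2 × m_spot
- Planned resection diameter = d + 2 × m_plan
- Salvage specimen diameter = planned diameter + c, where c is the true departure from plan

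Then:
- Specimen minus spot = c + 2 × (m_plan − m_spot)
- Specimen minus plan = c

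**No change of plan (c = 0), specimen minus spot:**

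| Light margin | Planned margin 5 mm | Planned margin 10 mm |
|---|---|---|
| 5 mm | 0 mm | +10 mm |
| 10 mm | −10 mm | 0 mm |

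The result is zero only when the two margins are equal. Otherwise the margin term alone can hide or imitate a change of up to 10 mm in diameter. For example, a salvage operation 5 mm smaller than planned (c = −5), with a 10 mm planned margin and a 5 mm light margin, gives −5 + 2 × (10 − 5) = +5 mm and reads as an enlargement. Comparing the specimen with the plan removes the margin term.

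**Flap cases.** With several parallel fibers over a curved surface, the protocol defines no spot diameter, so the written comparison has no reference value for these participants.

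**Number of cases.** 57 × 0.15 = 8.55, or about 9, with a 95% binomial range of 4 to 14. Using the 82% response cited in Section 12.1 instead, 57 × 0.18 = 10.3, with a range of 5 to 16. Both counts assume that every failure goes on to salvage surgery with a measurable specimen. With so few cases, random differences in margin may not average out. A systematic difference between light and surgical margins would not average out at any sample size.

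**The case against.** Several points can fairly be made for the text as it stands.

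- **The plan may be implied.** The data named in the purpose sentence could be read to include the surgical plan, since it is otherwise unclear why PDT-arm plans are required. That reading is possible, but it does not supply a comparison of specimen with plan. One would still have to be written.
- **The spot is not arbitrary.** It is the same participant's pre-treatment tumor plus a bounded margin, and a specimen far outside it does say something about the extent of salvage. This stands. A reader might infer that the comparison is uninformative. The documents do not support that, because they give no surgical margin that would show the spot and the planned resection to be far apart.
- **The item carries little weight.** It has no hypothesis, threshold or test. This stands too. A reader might infer that the choice of light margin would decide whether the trial supports giving PDT first. The documents contain no such decision rule, and the argument for PDT first rests mainly on failures being salvageable at all.
- **The flap is a fallback.** Eligibility criterion 7 in Section 5.1 requires unrestricted access for illumination, and no frequency of flap use is given. The gap is real, but its size is unknown.
- **The better comparison has limits.** Section 4.3 counts progression and local recurrence as failures, so specimen minus plan mixes tumor growth with any effect of PDT. The failures are a selected group, and the surgery-arm schedule (Table 3) lists no specimen diameter. The surgery arm therefore cannot serve as a like-for-like control.

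**Conclusion.** The point holds as a mismatch between the stated question and the specified comparator. The light spot is at best a rough proxy for the planned resection. Under the assumed 5 to 10 mm surgical margin, the proxy can be off by up to 10 mm in either direction with no change of plan. A wider or narrower range of surgical margins would change that figure, and it vanishes only if the two margins coincide, which the protocol neither states nor requires.

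The consequence is limited to a descriptive item in about 9 PDT failures. The primary non-inferiority test and the listed objectives are unaffected. The change is worth making because the plan is already required, and a planned diameter that was not recorded before treatment cannot be reliably recovered afterward.

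**What to change.** In Section 4.3:

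1. Have the surgeon record the planned resection diameter as part of the surgical plan already required, before randomization. The section sets no time for the plan, and the trial is open-label, so a plan made once the arm is known could be influenced by it.
2. Make the comparison salvage specimen diameter minus the same participant's planned diameter.
3. Keep spot size as a descriptive item, and say how the light field is recorded when the flap is used.
4. Report the result descriptively, with the number of participants contributing and a note that it reflects tumor growth or recurrence as well as any PDT effect. Planned against actual diameter in the surgery arm may be shown as context where specimen size is available, but not as a control.

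The cost is one added data field, a timing requirement for the plan and a reworded comparison sentence. No visit, procedure or treatment rule changes.

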4.4 TARGET ACCRUAL AND STUDY DURATION

A maximum of 114 participants at 3 sites, including RPCI, will be enrolled. Accrual is expected to take up to 4 years. Each participant is expected to be on the study for two years and will be followed according to NCCN guidelines.

5 PARTICIPANT SELECTION

The treating physician or his designee at each network site will determine eligibility.

5.1 INCLUSION CRITERIA

To be included in this study, participants must meet the following criteria:

1. Age \geq 18 years of age.
2. Have an ECOG Performance Status of \leq 2. Refer to **Appendix D**.
3. Participants with previously untreated T1/T2 N0 squamous cell carcinoma of the oral cavity with or without extension to the oropharynx.
4. Histologically confirmed squamous cell carcinoma of the target tumor(s).
5. Tumor thickness is 4 mm or less (measured clinically and/or by CT or MRI scan).
6. CT or MRI of the neck to confirm staging.
7. Tumor accessible for unrestricted illumination for photodynamic Therapy (PDT) (accessibility as determined by the physician).
8. Life expectancy of at least 12 months in the judgment of the physician.
9. Participants of child-bearing potential must agree to use adequate contraceptive methods (e.g., hormonal or barrier method of birth control; abstinence) prior to study entry and for the duration of study participation. Should a woman become pregnant or suspect she is pregnant while she is participating in this study, she should inform her treating physician immediately.
10. Participant or legal representative must understand the investigational nature of this study and sign an Institutional Review Board approved written informed consent form prior to receiving any study related procedure.

5.2 EXCLUSION CRITERIA

Participants will be excluded from this study for the following:

1. Those who have had chemotherapy or radiotherapy or targeted agents within 4 weeks (6 weeks for nitrosoureas or mitomycin C) prior to entering the study or those who have not recovered from adverse events due to agents administered more than 4 weeks earlier.
2. Those with known brain metastases should be excluded from this clinical trial because of their poor prognosis and because they often develop progressive neurologic dysfunction that would confound the evaluation of neurologic and other adverse events.
3. Those with porphyria or with known hypersensitivity to porphyrins or porphyrin-like compounds.
4. WBC < 4,000.
5. Those with impaired renal and/or hepatic function (total serum bilirubin >2 mg/dL, serum creatinine > 2 mg/dL, alkaline phosphatase (hepatic) or SGOT > 3 times the upper normal limit.
6. Diagnostic biopsy reveals perineural invasion (PNI) and/or lymphovascular invasion (LVI).
7. Uncontrolled intercurrent illness including, but not limited to, ongoing or active infection, symptomatic congestive heart failure, unstable angina pectoris, cardiac arrhythmia, or psychiatric illness/social situations that would limit compliance with study requirements.
8. Nodal disease as detected by clinical exam or CT.
9. Pregnant or nursing females.
10. Unwilling or unable to follow protocol requirements.
11. Any condition which in the Investigator's opinion deems the participant an unsuitable candidate to receive study drug.
12. Received an investigational agent within 30 days prior to enrollment.
13. Trismus or compromised airway.
14. Previous treatment in the target tumor area.

5.3 INCLUSION OF WOMEN AND MINORITIES

Both men and women and members of all races and ethnic groups are eligible for this study.

For Network Sites, refer to **Appendix A** for site specific instructions.

6 INVESTIGATIONAL PRODUCTS

6.1 ACTIVE SUBSTANCE AND SOURCE

The drug (photosensitizer) to be used in this study is 2-[1-hexyloxyethyl]-2-Devinyl pyropheophorbide-a (HPPH).

The HPPH is formulated for injection as follows:

Raw Materials for HPPH Formulation

Raw Material Name	Manufacturer Name/ Part Number Supplier Name/Part Number	Quantity in 2000 gram Batch
HPPH	Syngene/S14/FP/15/00053	2.40 gm
Sterile Water for Injection, USP	VWR/B. Braun Medical/L8501-01	1862.81 gm
190 Proof Ethanol*, USP	VWR/Spectrum/ET108-1LTGL	34.36 gm
Dextrose, Anhydrous, USP multi-compendial	VWR/JT Baker/JT1920-5	98.04 gm
Sodium Carbonate, NF	VWR/Spectrum/95035-752	0.26 gm
Tween 80*, USP	VWR/JT Baker/JT4117-4	2.13 gm
Total		2000.00 gm
pH adjustment after formulation		
Phosphoric Acid, NF, FCC	VWR/JT Baker/JT0262-1	0.082 gm
Sterile Water for Injection, USP	VWR/B. Braun Medical/L8501-01	8.12 gm

*Ethanol and Tween 80 percentages are volume/volume.

The concentration of HPPH vials will be 1.13 mg/mL.

6.2 DRUG SHIPMENT

The HPPH will be provided by Photolitec (Photolitec, LLC. Buffalo, NY) and shipped frozen, on dry ice to the participating sites.

Each receiving site will document the date of receipt of the shipment. Drug shipment records will be retained by the investigational pharmacist or designee.

6.3 STORAGE, PREPARATION AND STABILITY

Stability: The current drug has been found to be stable for up to 6 months. Long-term stability studies will be ongoing during the course of this study.

Storage and Preparation: HPPH vials will be stored frozen (a standard -20 C freezer), thawed at room temperature prior to administration, dispensed by the pharmacy of participating sites and administered within 4 hours of being removed from the freezer. The final dose should be protected from light.

Documentation: A careful record of each vial dispensed (including lot number) will be maintained. This record will also include the date of drug administration and the participant ID for whom the drug was made available.

6.4 HANDLING AND DISPOSAL

The manufacturer (Photolitic) will send the investigational drug to the RPCI research pharmacy and participating sites. Study drugs must be handled as cytotoxic agents and appropriate precautions taken per the institution's environmentally safe handling procedures. All investigational drugs will be dispensed in accordance with the Investigator's prescription or written order.

All products dispensed will be recorded on a product accountability record. Records of product lot numbers and dates received will be entered on a product accountability form. This record may be reviewed by the Sponsor's staff or representative. It is the Investigator's responsibility to ensure that an accurate record of investigational drug issued and returned is maintained.

Used vials (excess drug) will be destroyed according to standard practices at the site after properly accounting for the dispensing. Partially used vials of study drug will not be re-used for other participants.

Under no circumstances will the Investigator supply investigational drug to a third party or allow the investigational drug to be used in a manner other than as directed by this protocol.

